Motivational interviewing (MI) principles will be used throughout the PA coaching calls. MI is a key behavior change strategy that can elicit participants' own motivations and / or ambivalence toward PA⁸¹⁻⁸³. This helps individuals to explore and resolve their own, sometimes conflicting attitudes toward changing PA behaviors, building autonomy and internal awareness that is essential for long-term behavior change. To support topics discussed during the phone calls, participants will be mailed and/ or emailed materials including: 1) handouts describing appropriate exercise for people with osteoarthritis, tips on PA for people with arthritis (including pain management), instructions for different types of exercise (aerobic, strengthening, stretching), and example exercises. 2) A list of PA programs and resources adapted for their locality. 3) Worksheets for documenting PA goals.

Attention Control Intervention

We chose this type of control group to account for the effect of general attention provided by the PA Coach. This group will receive an intervention in the same "dose" (e.g., number and duration of phone calls and emails) as the OA-PCP group, but the content will not be PA-specific. During the first call, the Coach will discuss 2 topics, for which the amount of content parallels call #1 for the OA-PCP: What is OA? OA Diagnosis and OA Risk Factors. During the second call, the Coach will discuss the topic of Health Care Providers and Overview of OA Treatment Guidelines. Call topics for 3, 6, 9 and 12- month follow-up calls will be: Pain Medications, Mechanical Treatments (e.g., knee braces, footwear, joint protection), Complimentary and Alternative Therapies and discussion of OA and Mental Health, Sleep and Fatigue. Participants will be emailed or mailed (based on their preference) handouts with information on additional topics related to OA. The study team will ask participants to opt-in to receive follow-up monthly educational emails; if they prefer, they can receive this information via mail.

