6.4 STUDY INTERVENTION ADHERENCE

The study database will be used to track participants' completion of all assessment visits, as well as all intervention contacts. The coordinator will also maintain close communication with PA coach(es) regarding intervention delivery. If participants miss intervention calls, an unblinded study team member may assist the PA coach in attempting to reach the participant.

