Exploration of Mediators. We are interested in understanding the degree to which various facets of the OA-PCP contribute to improvements in PA and other outcomes. Because the mediating variables of interest (described above) pertain only to the OA-PCP group, our strategy will differ from a traditional mediation analysis approach in the context of a clinical trial. Specifically, we will use linear regression models to assess associations between potential mediating variables and outcomes among individuals in the OA-PCP group. Each potential mediator will be assessed individually, then we will fit a multivariable model including all variables with bivariate associations of $p \leq 0.1$. Analyses will be performed for both 6 and 12 month outcomes.

Exploration of Moderators. We will explore potential differential treatment effects based on participant characteristics, particularly gender, age and baseline PAVS score. The latter is of interest to help inform the inclusion criterion for a larger trial; if individuals with higher baseline PA (though not meeting DHHS recommendations) make little additional improvement in PA, we may focus on individuals with lower PA levels at screening. For assessment of differential treatment effects, we will conduct stratified analyses based on participant characteristics (e.g., men / women, age categories by decade, quartiles of baseline PAVS scores). We propose this strategy because the study is not powered to detect interactions between treatment group and participant characteristics. We will also use multivariable logistic regression^{104,105} and recursive partitioning (RP)^{106,107} to explore multidimensional subgroups that exhibit heterogeneous treatment effects; these analyses will focus on our a priori characteristics of interest but also explore additional variables.

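### The exploratory mediator regressions within the OA-PCP arm leave out the baseline value of the outcome, so a facet that does nothing can still appear associated with it

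*Combined protocol and SAP*

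**What the plan says.** Section 9.4, under Exploration of Mediators, gives the purpose: "We are interested in understanding the degree to which various facets of the OA-PCP contribute to improvements in PA and other outcomes". The method is that "we will use linear regression models to assess associations between potential mediating variables and outcomes among individuals in the OA-PCP group". The sequence is "Each potential mediator will be assessed individually, then we will fit a multivariable model including all variables with bivariate associations of" p ≤ 0.1, and "Analyses will be performed for both 6 and 12 month outcomes". No baseline covariate is named at either step, and the text does not say whether the outcome is the follow-up level or the change from baseline.

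The control arm is left out on this ground: "Because the mediating variables of interest (described above) pertain only to the OA-PCP group". Section 8.1 lists the mediators as number of OA-PCP calls completed, ratings of the calls, take-up of new activity resources, and ratings of those resources.

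Section 6.1 gives the attention control the same dose, described as "number and duration of phone calls and emails", with content that is not about physical activity. Section 6.4 says that the database tracks "completion of all assessment visits, as well as all intervention contacts", with no restriction by arm.

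**The concern.** The purpose is about contribution, but the regression measures how people who took up more of a facet differ from people who took up less. Those two groups may have differed before the first call. The joint model does not help, because it contains only other facets that arose after randomisation. Activity at entry is the obvious common cause. It is measured for every participant and is not used.

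For number of calls completed, the reason for omitting the control arm does not fit the design. Both arms have a first call, a second call, and calls at 3, 6, 9 and 12 months, which makes six. Controls therefore have a call count that reflects attendance without activity coaching.

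What is at stake is the reading of the exploratory facet results, not the test of efficacy.

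**Working it through.** **Inputs from the documents.** 120 per arm and 10% attrition (Section 9.2), so 120 × 0.9 = 108 analysed; two-sided 0.05 (Section 9.4); screen at p ≤ 0.1.

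**The plan's own figure.** There is none for the mediators. The power statement in Section 9.2 reproduces with 108 per arm: 0.38 × √(108/2) = 2.792 and Φ(2.792 − 1.96) = 79.7%, against a stated 80%. This confirms the analysed number and has no other bearing here.

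**Assumptions not in the documents.** ρ is the correlation of baseline with follow-up, 0.5 to 0.7. r is the correlation of baseline with the facet, 0.1 to 0.3. Variances are equal at the two times. The facet has no effect and is linked to the outcome only through measured baseline.

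**Formulas.**
- Follow-up level: corr(facet, outcome) = rρ.
- Change: covariance r(ρ − 1), variance 2(1 − ρ), so corr = −r√((1 − ρ)/2).
- δ = √(108 − 3) × atanh(corr) = 10.247 × atanh(corr).
- Rejection at 0.05 ≈ Φ(δ − 1.96) + Φ(−δ − 1.96). At 0.1, replace 1.96 by 1.645.

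Example with ρ = 0.7, r = 0.3. For the level, corr = 0.21, δ = 2.184 and rejection is Φ(0.224) = 58.9%. For change, corr = −0.116, δ = −1.196 and rejection is 22.3%, of which 0.1 points favour the facet.

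| ρ | r | Level, p ≤ 0.05 | Level, p ≤ 0.1 | Change, p ≤ 0.05 | of which favouring the facet |
|---|---|---|---|---|---|
| 0.5 | 0.1 | 8.1% | 14.4% | 8.1% | 0.7% |
| 0.5 | 0.2 | 17.7% | 27.3% | 17.7% | 0.1% |
| 0.5 | 0.3 | 34.1% | 46.2% | 34.1% | 0.0% |
| 0.7 | 0.1 | 11.1% | 18.6% | 6.8% | 0.9% |
| 0.7 | 0.2 | 30.3% | 42.1% | 12.5% | 0.3% |
| 0.7 | 0.3 | 58.9% | 70.5% | 22.3% | 0.1% |

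Simulation agrees to within about a point, giving ranges of about 8% to 60% (level) and 7% to 35% (change). With the baseline outcome in the model, simulated rejection is about 5% throughout.

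**Other routes into attendance.** A separate simulation used 0 to 6 calls, ρ = 0.6, a latent attendance–activity correlation of 0.3 and no call effect. Rejection at 0.05 was:

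| What drives attendance | Level | Change | Level with baseline added |
|---|---|---|---|
| Measured baseline | 38.9% | 24.2% (negative) | 4.9% |
| Stable activity trait | 60.5% | 4.6% | 19.8% |
| Activity during follow-up | 42.5% | 51.8% | 61.4% |

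Baseline adjustment is a full cure only in the first row.

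**Two-arm slope difference for calls completed.** With the same selection in both arms, rejection is 4.6% to 5.2% across latent correlations of 0 to 0.5. With 0.3 in OA-PCP and 0.1 or 0 in control, it is 17.6% or 34.2%; adding baseline lowers these to 7.9% and 12.4%.

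**Precision.** Assume a true standardised slope of 0.2, ρ = 0.6 and baseline in the model. Single arm: δ = 0.2/√(1 − 0.36) × √108 = 2.598, power Φ(0.638) = 74%. Slope difference: δ = 2.598/√2 = 1.837, power Φ(−0.123) = 45%. Simulation gave about 73% and 44%.

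**The case against.** The analysis is labelled exploratory, says that it departs from ordinary mediation analysis, and already speaks of associations. The correlations behind the figures are assumed, and even the sign of the link between attendance and baseline activity is undocumented. At r = 0.1 the screen passes 14% to 19% of null facets against a nominal 10%, which is modest. All of this stands, and it limits the weight of the point.

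Three stronger readings are tempting, and the documents do not support them.

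- A reader might infer that the analysis will credit the calls with benefit they did not produce. That follows if the outcome is the follow-up level. With a change score and selection through measured baseline, at most about 1% of trials give a false result in the calls' favour; nearly all the error runs the other way. Section 9.4 leaves the outcome form open.
- A reader might infer that refinement of OA-PCP for the larger trial would be misdirected. Sections 4.1 and 9.1 base refinement on feedback from patients, clinic personnel and community representatives. Nothing ties it to these regressions.
- A reader might infer that the control arm isolates attendance selection. It does so only if selection is similar in both arms, and the arms differ in content and in the activity tracker. It also bears directly on only one of the listed mediators, calls completed.

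None of this gives a reason to leave out a baseline value that is already collected.

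**Conclusion.** The point holds as a limited one. The within-arm mediator models use no baseline outcome at either step, although the stated aim is "understanding the degree to which various facets of the OA-PCP contribute to improvements in PA and other outcomes". Under the assumed correlations, false rejection at 0.05 is about 8% to 60% in the facet's favour for a follow-up-level outcome, and about 7% to 35%, mostly against it, for a change score. Those directions assume a positive link acting through measured baseline; other mechanisms change both rate and direction. Adding the baseline outcome removes that route but not confounding by unmeasured motivation or health, or attendance that follows activity during the trial. The between-arm efficacy analysis is not affected.

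**What to change.** In Section 9.4, Exploration of Mediators:

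1. State the outcome form, and include the baseline value of the outcome in both the single-facet and the multivariable models. Say that this deals with confounding through measured baseline only.
2. For number of calls completed, add a sensitivity analysis in both arms: outcome on group, calls completed, group × calls completed and baseline outcome. State that the slope difference removes attendance selection only if selection is similar in the two arms, and that it is markedly less precise than the single-arm slope.
3. Report every result as an exploratory association, not as the contribution of a facet, and bring the purpose sentence into line with that.

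The cost is a few sentences and a few more models. Baseline outcomes are in the schedule of activities and contacts are tracked in the database, so no new data are needed. Sample size and the primary analysis do not change.

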Patient Global Impression of Change. We will use this scale to evaluate participants' perspectives on overall changes in their joint pain during the study period. This measure asks participants to describe their change in pain on a 7-point rating scale with the following options: "very much improved," "much improved," "minimally improved," "no change," "minimally worse," "much worse," and "very much worse." This scale has been widely used in clinical trials of chronic pain and is recommended by IMMPACT.

Pain Medication Use. Pain medications are a common treatment for patients with OA, and some patients seek to reduce their use; therefore we have included this as an exploratory outcome. We will assess pain medication use using methods we have used successfully in previous studies. We will ask participants to bring to the telephone all medications (prescription and non-prescription) they are currently taking for their arthritis symptoms. For each medication, the study team will record the medication name, medication class, frequency of taking the medication.

PROMIS Sleep Disturbance – Short Form 4a. The PROMIS adult sleep related impairment item bank focuses on self-reported perceptions of sleep quality, sleep depth, and restoration associated with sleep. It assesses sleep-related impairment over the past seven days. This scale includes 4 items, each measured on a 5-point Likert scale.

Potential Mediators and Moderators of Intervention Effects:

We are interested in understanding the roles of various “active ingredients” of the OA-PCP (mediators), as well as potential patient characteristics that are associated with differential effectiveness (moderators). With respect to mediators, we will assess number of OA-PCP calls completed, participants’ ratings of satisfaction and helpfulness of the calls (single item numeric rating scales of 0-10), indicators of whether participants engaged with new group-based or self-directed PA resources during the study, and participants’ ratings of satisfaction and helpfulness of any new PA resources they have tried. These variables will be assessed at both 6 and 12 months. With respect to moderators, we are particularly interested in variables of age, gender and level of baseline PA, but we will also conduct additional exploratory analyses of heterogeneity of treatment effects, as described below.

Participant Characteristics:

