9.2 SAMPLE SIZE DETERMINATION

We note that this study is an extended exploratory phase, in which we are interested in obtaining estimates of efficacy that will inform a larger trial that is adequately powered to detect clinically meaningful differences in MVPA. Our sample size was selected on the basis of feasibility for this exploratory study and involvement of a sufficient number participants to adequately assess intervention and study procedures. We provide here a description of expected statistical power for this sample size. Based on previous research on PA

interventions for OA^{98,99}, we expect an effect

size of 0.3-0.7, though have examined a range of possible values from 0.2-0.8 (Table 2). We also account for 10% attrition, based on our prior work. A sample size of 240 participants (120 per group) will provide approximately 80% power at 5% level of significance to detect a small-to-medium effect size of 0.38 or greater for the difference in minutes of MVPA between intervention and control groups, accounting for expected attrition.

$\alpha=0.05$	Power=80%	Power=85%	Power=90%	Power=95%
Effect size	Sample size	Sample size	Sample size	Sample size
0.20	787	900	1053	1301
0.30	351	401	469	579
0.40	198	226	265	327
0.50	128	146	170	210
0.60	90	102	120	148
0.70	68	76	88	110
0.80	52	60	68	84

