9.4 STATISTICAL ANALYSES PLAN

Preliminary analyses will include generating descriptive statistics for demographic variables, as well as baseline characteristics and follow-up measures. This includes means and standard deviations for continuous variables, and frequencies and percentages for categorical variables. Ranges will also be examined for outliers and to ensure data integrity. Demographics and baseline characteristics will also be described separately by randomized group.

We hypothesize that participants receiving the OA-PCP will have greater improvement in MVPA compared with the attention control group at 6 and 12 months. To determine the effects of the intervention on MVPA, repeated measures will be analyzed using linear mixed effects models, with clinic included as a random effect, to estimate mean change and 95% confidence intervals in MVPA from baseline to 6-month and 12-month time points. This model will account for intra-person clustering for the repeated measures, including a group x time effect. We will use the same modeling strategy for continuous secondary and exploratory outcomes. An advantage of this modeling approach is that it uses all available data; participants are not dropped if they miss a time point. This approach will reduce the overall amount of missing data and could eliminate the need for imputation of missing repeated outcomes¹⁰⁰. However, if we find that missing data are related to measured patient factors (i.e., missing not at random [MNAR]), we will carry out sensitivity analyses by imputing missing values under the MNAR scenario and examining the results. The SAS procedure PROC MI has several options for using multiple imputation in sensitivity analyses based on pattern-mixture models for MNAR data, which model the distribution of a response as the mixture of a distribution of the observed responses and a distribution of the missing responses¹⁰¹. Multiple imputation has the advantage of providing a framework for incorporating information from these variables, while preserving a parsimonious main treatment effect model^{102, 103}. Analyses will be conducted on an intent-to-treat basis and carried out using SAS 9.4 (SAS Institute Inc., Cary, NC). Tests will be two-sided and considered significant at the 0.05 level.

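### The exploratory mediator regressions in the OA-PCP arm leave out the baseline value of the outcome, so any link between baseline activity and engagement biases them, in a direction that depends on an outcome form the plan does not state

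*Combined protocol and SAP*

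**What the plan says.** Section 9.4 (Exploration of Mediators) plans "linear regression models to assess associations between potential mediating variables and outcomes among individuals in the OA-PCP group". Each candidate is tested alone; "then we will fit a multivariable model including all variables with bivariate associations of" p ≤ 0.1. This is done for 6-month and 12-month outcomes. No covariate is named, and the text does not say whether an outcome enters as a follow-up level or as a change from baseline. The paragraph says openly that it departs from a conventional mediation analysis.

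Section 8.1 lists the mediators: number of OA-PCP calls completed, ratings of those calls, "indicators of whether participants engaged with new group-based or self-directed PA resources during the study", and ratings of any resources tried. It calls them active ingredients of the programme and says they are assessed at 6 and 12 months. In the schedule of activities (section 1.3), the row for mediators and moderators is marked only at Visit 11, the 12-month visit.

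Accelerometer MVPA and WOMAC are collected at baseline in all participants (sections 1.3 and 8.1). In the exploratory part of section 9.4, baseline activity appears only as a moderator, through the PAVS score.

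**The concern.** Completing calls and trying resources are not randomised. They are things participants do after randomisation, and may be linked to how active they already were. Baseline MVPA also predicts follow-up MVPA. A regression of the outcome on such a mediator without baseline therefore mixes any effect of the component with differences that existed before the programme began.

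The main model in section 9.4 handles baseline as one of the repeated measures, but the mediator analysis is a separate linear regression and does not inherit that. At stake is the reading of the exploratory results: a component that does nothing can appear to help, or a useful one can appear inert or harmful. The randomised comparison of OA-PCP with attention control is not touched.

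**Working it through.** **The plan's own figure.** The only stated power is for the primary comparison: "A sample size of 240 participants (120 per group) will provide approximately 80% power at 5% level of significance" for an "effect size of 0.38 or greater for the difference in minutes of MVPA", where "We also account for 10% attrition, based on our prior work". With 120 × 0.9 = 108 per arm, d = 0.38 and two-sided alpha 0.05, power is 0.797 (0.794 by the noncentral t), so the figure reproduces. No figure is given for the mediator analysis.

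**Inputs for the check.**
- n = 108 in the OA-PCP arm, from the planned attrition. Using the share with valid follow-up accelerometer data in the Aim 2 pilot (52 of 60, section 8.1) gives 120 × 52/60 = 104, which changes little.
- Screening threshold p ≤ 0.1 (section 9.4).
- r, the correlation of the mediator with baseline MVPA: not in the documents. Assumed 0 to 0.4.
- ρ, the correlation of baseline with follow-up MVPA: not in the documents. Assumed 0.5 to 0.7.
- The mediator has no effect, and baseline and follow-up have equal variance.

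**Formulas.** The correlation induced between a null mediator and the outcome is
- follow-up level: r × ρ
- change from baseline: −r × √((1 − ρ)/2)

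At r = 0.3 and ρ = 0.6 these are 0.3 × 0.6 = 0.18 and −0.3 × √0.2 = −0.134.

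By the Fisher z approximation with n = 108, the standard error is 1/√105 = 0.0976.
- Level: atanh(0.18)/0.0976 = 1.865, and P(p ≤ 0.1) ≈ Φ(1.865 − 1.645) = 0.59.
- Change: atanh(0.134)/0.0976 = 1.383, and P(p ≤ 0.1) ≈ Φ(1.383 − 1.645) = 0.40, almost all in the negative direction.

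At n = 104 the same steps give 0.57 and 0.39.

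**Range.** Simulation with 4,000 runs per row and ρ value, n = 108. Entries are the percentage of runs in which the null mediator passes p ≤ 0.1; each pair is ρ = 0.5 / ρ = 0.7.

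| r | Level, unadjusted | Change, unadjusted | Baseline as covariate |
|---|---|---|---|
| 0 | 10.0 / 9.7 | 9.2 / 9.9 | 9.9 / 10.1 |
| 0.1 | 14.0 / 18.2 | 14.4 / 12.7 | 9.5 / 10.2 |
| 0.2 | 28.7 / 43.3 | 27.2 / 20.1 | 9.6 / 9.1 |
| 0.3 | 47.3 / 70.4 | 45.7 / 32.1 | 10.1 / 9.7 |
| 0.4 | 67.3 / 91.4 | 65.4 / 49.9 | 9.2 / 9.9 |

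Mean slopes are positive for level and negative for change when r > 0. With negative r both signs reverse. With baseline in the model the mean slope is about zero. The mediator coefficient is then also the same for level and change, because subtracting a covariate from the outcome alters only that covariate's own coefficient.

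**What adjustment does not remove.** Add an unmeasured factor such as motivation, independent of baseline, with loading 0.2, 0.3 or 0.4 on both mediator and outcome (assumed; here r = 0.2 and ρ = 0.6). The baseline-adjusted model then still passes a null mediator in 14%, 33% and 69% of runs.

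**The case against.** The strongest reply has four parts.

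1. **Direction.** A reader might infer that more active participants will make calls and resources look effective. The documents do not support that. The outcome form is not stated, and change is at least as natural a reading: the hypotheses speak of improvement and the main model estimates mean change. Under change, a positive mediator-baseline correlation makes null components look worse. This stands, and the point is made without a direction.

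2. **Size.** No passage links baseline activity to calls or resource use. The correlation could be zero or negative: the resource item concerns new resources, which less active people may need more, and everyone enrolled reports under 150 minutes a week. This stands as a limit on the percentages. It does not defend leaving out a covariate that is already collected.

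3. **Stakes.** A reader might infer that components will be kept or dropped on these results. Sections 4.1 and 9.1 tie refinement to feedback from patients, clinic personnel and community representatives, not to these regressions. The analysis is labelled exploration and described in terms of associations. This stands and limits the importance.

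4. **Neighbouring issues.** The p ≤ 0.1 screen does not cause the confounding. It is a separate matter: with seven independent null mediators (an assumed count), 1 − 0.9⁷ = 0.52 is the chance that at least one passes. A reader might also infer that the one-arm design is unjustified because controls get the same "number and duration of phone calls and emails". But the call mediators are defined on OA-PCP calls, and control calls have different content. Only resource use could readily be asked in both arms.

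**Conclusion.** The concern holds in a limited form. The mediator regressions omit the baseline value of the outcome, which the trial collects. They are therefore biased whenever baseline activity is correlated with engagement, with a sign that depends on an outcome form the plan does not state.

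Under the assumed correlations (r from 0.1 to 0.4, ρ from 0.5 to 0.7, n = 108), a mediator with no effect passes p ≤ 0.1 in about 14% to 91% of cases for level and 13% to 65% for change, against about 10% with adjustment. At r = 0 there is nothing to correct. These figures illustrate what could happen and are not forecasts for this trial.

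A reader might also infer that baseline adjustment would allow active ingredients to be identified. It would not: motivation remains, and mediators assessed at the same visits as the outcomes leave reverse causation open. The analysis is exploratory and the primary comparison is unaffected, so this is worthwhile to correct but not critical.

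**What to change.** In section 9.4 (Exploration of Mediators):

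- State which outcomes are analysed and whether each enters as follow-up level or change.
- Include the baseline value of the outcome in every individual and multivariable mediator regression. Patient Global Impression of Change has no baseline; name a substitute such as baseline WOMAC pain.
- If a p ≤ 0.1 screen is kept, apply it to the baseline-adjusted associations.
- Report the results as associations, naming motivation and same-time measurement as remaining sources of bias.

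Separately, reconcile section 8.1 (mediators at 6 and 12 months) with section 1.3 (Visit 11 only). The 6-month analysis in section 9.4 depends on the answer.

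Two further changes may look attractive but should not be adopted without more thought. A single model with all listed mediators fails on the resource ratings, which exist only for people who tried a resource. Using only 6-month mediators for 12-month outcomes ignores the later calls and needs 6-month data that the schedule does not show.

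The cost is SAP wording and one covariate per model, with no new data. Participants without valid baseline accelerometer data drop out of a complete-case MVPA model; in the Aim 2 pilot 57 of 60 had valid data.

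### The exploratory mediator analysis screens candidates at p ≤ 0.1 and refits the survivors on the same data, so null and weak components that are retained look stronger than they are; a surviving resource rating can also remove non-users

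*Combined protocol and SAP*

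**What the plan says.** Section 9.4, under Exploration of Mediators, uses linear regression "to assess associations between potential mediating variables and outcomes among individuals in the OA-PCP group". The procedure has two steps: "Each potential mediator will be assessed individually, then we will fit a multivariable model including all variables with bivariate associations of" p ≤ 0.1. It is applied to 6-month and 12-month outcomes, for PA and for other outcomes that are not listed. No sample split, shrinkage, validation, post-selection correction or multiplicity rule is given.

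The candidates are in Section 8.1, under Potential Mediators and Moderators:
- "number of OA-PCP calls completed";
- satisfaction with the calls and helpfulness of the calls;
- "indicators of whether participants engaged with new group-based or self-directed PA resources during the study";
- "participants’ ratings of satisfaction and helpfulness of any new PA resources they have tried".

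The general rule in Section 9.4 is "Tests will be two-sided and considered significant at the 0.05 level", with no exception for mediators. Confidence intervals at 95% are specified for the MVPA mixed model. None are specified for the mediator models.

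**The concern.** A variable enters the final model because its association in this sample was large enough to pass the screen. The final model then estimates that association from the same sample as though it had been chosen beforehand. For a component with no effect or a weak one, passing requires a favourable chance deviation, which the refit carries forward. A reader who sees only the surviving terms would judge such components too favourably.

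The stated purpose is to learn how far each facet of OA-PCP contributes, which is an estimation question. The study is also meant to inform a larger trial, so an exaggerated component could receive undue weight in the next version of the programme.

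A second difficulty comes from the data structure. Someone who tried no new resource has nothing to rate. A model that includes a resource rating may therefore describe a different group of people from a model without one.

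**Working it through.** **Inputs.** Section 9.2 gives 120 per group and 10% attrition: 120 × 0.9 = 108 in the OA-PCP arm. Candidates from Section 8.1: calls completed (1), call ratings (2), engagement indicators (1-2), resource ratings (1-2), so 5 to 7. Correlations between candidates and true effect sizes are not in the documents and are assumed below.

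**The plan's own figure.** Section 9.2 states about 80% power for an effect size of 0.38. With 108 per arm, power = Φ(0.38 × √(108/2) − 1.96) = Φ(2.792 − 1.960) = Φ(0.832) = 79.7%. This reproduces, so 108 is a fair size for the within-arm analysis. The plan gives no error rate for the mediator analysis.

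**Null candidates, uncorrelated.**
- Chance that at least one passes the screen: 1 − 0.9^k = 41% (k = 5) to 52% (k = 7), per outcome and time point.
- Chance that a retained null is significant in the final model: about 0.05/0.10 = 50%.
- Unconditional error per candidate: 0.10 × 0.50 = 5%. The screen does not raise it.
- At least one false positive: 1 − 0.95^k = 23% to 30%, whether or not the screen is used; over two time points, 1 − 0.95^(2k) = 40% to 51% if tests are independent. This comes from the number of tests.

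**Null candidates, correlated.** The stated rule was simulated with n = 108, normal variables, a common correlation and 8,000 data sets per setting. Entries are k = 5 / k = 7, in percent.

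| Assumed correlation | At least one retained | Retained null significant at 0.05 | Unconditional error per candidate | Any false positive, screened | Any false positive, full model |
|---|---|---|---|---|---|
| 0 | 41.1 / 52.5 | 48.5 / 49.6 | 4.9 / 5.0 | 21.8 / 29.8 | 21.8 / 29.5 |
| 0.3 | 38.2 / 48.2 | 35.4 / 31.2 | 3.6 / 3.2 | 16.8 / 20.4 | 22.2 / 29.0 |
| 0.5 | 33.9 / 40.0 | 21.9 / 17.3 | 2.2 / 1.7 | 11.0 / 11.5 | 21.6 / 28.3 |
| 0.7 | 27.0 / 32.6 | 11.8 / 7.8 | 1.2 / 0.8 | 5.9 / 5.5 | 21.1 / 28.7 |

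**One true component.** To pass p ≤ 0.1 with n = 108, t must reach 1.659 on 106 degrees of freedom, which is an observed correlation of 1.659/√(1.659² + 106) = 0.159. A true correlation of 0.10 can pass in the right direction only if it is overestimated by a factor of about 1.6 or more in the bivariate step. Simulation of the whole rule with k = 6 and the other candidates null:

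| True standardized effect | Chance retained | Mean estimate when retained, correlation 0 / 0.3 / 0.5 / 0.7 | Full model mean |
|---|---|---|---|
| 0.1 | 27-28% | 0.21 / 0.19 / 0.15 / 0.13 | 0.10 |
| 0.2 | 66-68% | 0.25 / 0.22 / 0.19 / 0.18 | 0.20 |
| 0.3 | 94% | 0.31 / 0.28 / 0.26 / 0.27 | 0.30 |

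The 0.7 entry for a true effect of 0.1 is 0.13 to 0.14 across runs. Inflation is large at 0.1, at most about 1.2 times at 0.2, and essentially absent at 0.3. The full model is unbiased throughout, with nominal coverage of 94-95% at the correlations where it was checked (0 to 0.6).

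**Resource ratings.** Suppose a rating survives and non-users are left missing. Ordinary regression then keeps only participants who tried a resource. If engagement is one indicator, it equals 1 for everyone and cannot be estimated. If it is two (group-based, self-directed), nobody is left with both at zero, so only types of user can be compared. The analysed sample also changes with whichever variables survive, so the 6-month and 12-month models may describe different people.

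**The case against.** The strongest reply is that the plan calls this exploration. Section 9.2 describes an extended exploratory phase, the mediator text speaks of associations, and it concedes that the strategy is not a traditional mediation analysis. H1 and H2 contain no mediator hypothesis, and no decision follows from a retained variable. This stands, and it keeps the point minor. It does not justify an avoidable bias when an unscreened model uses the same data.

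The high conditional error also depends on uncorrelated candidates. Satisfaction and helpfulness ratings of the same calls are likely to be correlated, so the lower rows of the first table are the more plausible ones. This stands too.

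A reader might infer several stronger things that the documents and figures do not support:
- *The screen inflates family-wise error.* It does not; the screened rule is level with or below the full model in every row, apart from simulation noise.
- *All retained effects are exaggerated.* Only null and weak ones are.
- *The mediator confidence intervals are wrong.* The plan promises none for these models. For retained true effects, nominal coverage would be about 89-99% in the settings tried; the failure concerns retained nulls.
- *This is how the trial will decide which components work.* Refinement also rests on patient and clinic feedback (Section 4.1), open-ended acceptability questions (Section 8.1) and the record of resource contacts (Section 6.1).

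Finally, the loss of non-users is conditional. The plan does not say how non-users are coded, and a rating must first survive the screen.

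**Conclusion.** The concern holds in a limited form. Conditional on being retained, null and weak components are overstated and their nominal p-values are not valid. A retained null is significant at 0.05 about 50% of the time with uncorrelated candidates and about 7-12% at a correlation of 0.7, against a nominal 5%. A true effect of 0.1 is reported at about 0.13-0.21; at 0.2-0.3 there is little or no inflation. These figures assume 108 analysed participants, 5 to 7 candidates, normal variables and a common correlation.

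Multiplicity is a separate and larger matter, set by the number of candidates, outcomes and time points. The resource-rating problem follows from the definitions in Section 8.1 if non-users are left missing. Severity is minor, and the primary MVPA analysis is not affected.

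**What to change.** In Section 9.4, delete the p ≤ 0.1 step and write:
- For each listed outcome and time point, one prespecified linear model in the OA-PCP arm contains calls completed, call satisfaction, call helpfulness and the engagement indicators, whatever their bivariate p-values.
- Every coefficient and every bivariate result is reported, and all p-values are labelled descriptive and hypothesis-generating. The label is needed because the full model still gives at least one false positive in about 21-22% of analyses with five terms.
- Satisfaction with and helpfulness of resources are fitted in a separate model among participants who tried one.
- Call ratings are defined only for participants who completed at least one call. Sections 6.4 and 7.1 allow for missed calls and discontinuation, so the number excluded for this reason is reported.

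The cost is wording; no new data are needed. The downside is slightly wider intervals from keeping all terms: about 5 terms on 108 participants, or 108/5 ≈ 22 per term.
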